## **8. STATISTICAL CONSIDERATIONS AND ANALYSIS PLAN**

This is a randomized, double-blinded, placebo-controlled clinical trial designed to assess the impact of hydroxychloroquine to reduce the risk of progression from Stage 1 T1D (multiple autoantibodies, normal glucose tolerance) to Stage 2 (abnormal glucose tolerance) or Stage 3 (clinical diagnosis of diabetes). Eligible participants will be randomized in a 2:1 allocation ratio to treatment with hydroxychloroquine vs. placebo. Randomization will be stratified by two factors to ensure balance in the proportions who are randomized to each of the treatment arms: (1) prior enrollment on a T1D prevention trial and (2) age (<8 vs. ≥8 yrs. old). Specifically, participants will be randomized to hydroxychloroquine vs. placebo with stratification on whether they: (1) had prior enrollment on a T1D prevention trial and received placebo vs. had prior enrollment on a T1D prevention trial and received active therapy vs. had no prior enrollment on a T1D prevention trial, and (2) are younger than 8 years old vs. 8 years old or older. Age is a known significant factor in relation to clinical outcomes of interest even in the T1D prevention setting. Further, this cutoff of 8 years old at study entry was selected based on analyses that showed a significant effect modification on clinical outcomes based on this.

Analyses of study data will be conducted to address the primary and secondary objectives of the trial, other stated objectives, and other interrelationships among elements of study data of interest to the investigators and of relevance to the objectives of the study. Analyses by age, gender, and race/ethnicity, as appropriate, are also planned.

All analyses will be conducted under an intention-to-treat principle, whereby all outcome data in all randomized participants will be included in all analyses, as appropriate. Details of the analysis can be found within the statistical analysis plan.

### **8.1. Primary Outcome**

The primary outcome is the elapsed time from random treatment assignment to the development of confirmed abnormal glucose tolerance or clinical diabetes among those enrolled in the primary analysis cohort consisting of participants with islet cell autoimmunity and absence of metabolic abnormalities (normal OGTT). The date of the confirmatory abnormal OGTT or diabetes will be considered as the date of reaching these study endpoints. It is expected that abnormal glucose tolerance will be detected prior to diabetes onset by OGTT; however, the presence of diabetes, without a previous abnormal

OGTT, is also considered an endpoint.

While the hydroxychloroquine prevention study is ongoing, any participant who has progressed to abnormal glucose tolerance will have met the primary endpoint criteria. These participants who have developed abnormal glucose tolerance but have not progressed to Stage 3 T1D will have the option to remain in this study without further therapy; they will receive close monitoring and safety assessments until the development of Stage 3 T1D (clinical diabetes) or until they enroll in another clinical trial, whichever comes first.

The study endpoint is realized with either confirmed OGTT criteria for abnormal glucose tolerance or diabetes or clinical criteria for diabetes.

OGTT criteria for abnormal glucose tolerance or diabetes:

The presence of an OGTT consistent with impaired glucose tolerance or diabetes on two sequential dates. A participant with abnormal glucose tolerance or diabetes on an OGTT should undergo a repeat OGTT as soon as possible, but no less than one day apart. Aim to repeat within one month.

The definition of abnormal glucose tolerance is:

- a. Fasting plasma glucose  $\geq 110$  mg/dL (6.1 mmol/L) and  $< 126$  mg/dL (7.0 mmol/L), or
- b. 2 hour plasma glucose  $\geq 140$  mg/dL (7.8 mmol/L) and  $< 200$  mg/dl (11.1 mmol/L), or
- c. 30, 60, 90 minute plasma glucose during OGTT  $\geq 200$  mg/dL (11.1 mmol/L).

Criteria for Diabetes Diagnosis:

- A. Diabetic Ketoacidosis (DKA) or unequivocally symptomatic\* AND at least one of the following:
- 1) Random glucose  $\geq 200$  mg/dl (11.1 mmol/L) OR
  - 2) Fasting Glucose  $\geq 126$  mg/dl (7.0 mmol/L) OR
  - 3) OGTT = diabetic\*\* OR
  - 4) HbA1C  $\geq 6.5\%$ .

\*Unequivocal symptoms: Severe/persistent polyuria, polydipsia and/or significant unexplained weight loss

\*\*A diabetic OGTT is defined as:

- a. Fasting plasma glucose  $\geq 126$  mg/dL (7.0 mmol/L) AND/OR
- b. 2 hour plasma glucose  $\geq 200$  mg/dL (11.1 mmol/L)

B. If not unequivocally symptomatic, two separate objective measures are required for diagnosis. These tests must occur within 1 year of each other and must be consecutive, defined as without an intervening non-diabetic OGTT.

- **The preferred objective measures for diagnosis are:**

\* 2 diabetic OGTTs, not on the same day (the confirmatory OGTT is the date of

diagnosis)

- However, if an individual is diagnosed without the consecutive OGTTs, the following also constitute diagnosis in TrialNet:
  - \* Diabetic OGTT + FPG  $\geq$  126 mg/dl [7 mmol/L] (not on the same day)
  - \* Diabetic OGTT + HbA1c  $\geq$  6.5% (these may be on the same day)
  - \* FPG  $\geq$  126 mg/dl [7 mmol/L] + HbA1c  $\geq$  6.5% (these may be on the same day)

The TrialNet Eligibility and Events Committee will review and adjudicate any cases with only a single objective measure, cases which do not meet the criteria above, and/or cases which have uncertain results of tests and/or the test procedures. Qualifying glucose values should be from laboratory tests, rather than capillary blood glucose meter readings.

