As illustrated in Figure 2, data also suggest that the rate of progression through each stage is age dependent, with younger individuals progressing more rapidly.

Overall, about 40% of individuals at Stage 1 T1D will progress to Stage 2 within two years (Figure 3), and almost 70% of those at Stage 2 will develop clinically overt T1D (Stage 3) within four years (Figure 4). More children than adults will be expected to progress from Stage 1 to 2 and from Stage 2 to Stage 3 during these time periods.

[figure not shown]

FIGURE 3: Two year risk of confirmed abnormal glucose tolerance is 38% among individuals with multiple autoantibody positivity and normal glucose tolerance at baseline in the TN01 Pathway to Prevention Study.

[figure not shown]

Figure 4: Four year risk of diabetes onset is 68% among individuals with multiple autoantibody positivity and confirmed abnormal glucose tolerance in the TN01 Natural History/Pathway to Prevention Study.

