### 2.1.3 Disease-Modifying Therapy in T1D

Since the first use of insulin in 1922, treatment of T1D has been targeted at controlling the symptoms and consequences of hyperglycemia. This is analogous to symptom control for individuals with rheumatoid and juvenile arthritis, where the aim of therapy was previously to control pain and/or provide devices to adapt to the presence of disability. Yet, control of symptoms of arthritis - and almost all other autoimmune disease - is no longer the primary aim of treatment; instead, the standard of care is disease-modifying therapy with the intent to fundamentally alter the course of the condition. This approach has dramatically changed the lives of those with these autoimmune diseases. The aim of disease-modifying therapy in T1D is the same: to move away from symptom management (e.g., glycemic control) as the mainstay of treatment and find approaches to alter the disease course.

At least four therapies have been shown to have some effect on preservation of insulin secretion at Stage 3 (clinical onset) of disease. Two of these (Abatacept or CTLA4-Ig) and Teplizumab (Anti-CD3) are now under trial at Stage 1 and Stage 2 of T1D, testing the concept that treating earlier in disease is likely to have greater benefits. Early treatment has been shown to be useful in other autoimmune diseases, such as juvenile arthritis. Moreover, successful application of disease-modifying therapy at Stage 1 or Stage 2 of T1D would have clear clinical benefit by the delay or prevention of clinically overt disease (Stage 3).

In summary, the rationale for this study is that individuals at Stage 1 T1D, defined as those with immunologic markers and normal glucose tolerance, will inevitably develop Stage 3 or clinically overt

T1D. Prior to development of clinical T1D, they will progress from Stage 1 T1D (normal glucose tolerance) to Stage 2 T1D (abnormal glucose tolerance). Intervention early in the course of disease is likely to be more effective than intervention in those with abnormal glucose tolerance or clinical T1D. As described below, this is particularly likely to be true with the therapy being tested in this trial – hydroxychloroquine.

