### **3.3.1. Inclusion Criteria**

Study participants must be or have:

1. A participant in TrialNet Pathway to Prevention Study (TN01).
2. Age  $\geq$  3 years at the time of randomization in this trial.
3. Willing to provide informed consent or, if the participant is <18 years of age, have a parent or legal guardian provide informed consent.
4. Normal glucose tolerance by OGTT within 7 weeks (no more than 52 days) prior to randomization. If previous abnormal glucose tolerance, has had two consecutive OGTTs with normal glucose tolerance:
  - a. Fasting plasma glucose < 110 mg/dL (6.1 mmol/L), and
  - b. 2-hour plasma glucose <140 mg/dL (7.8 mmol/L), and

- c. 30, 60, and 90 minute value on OGTT < 200 mg/dL (11.1 mmol/L).
5. Two or more diabetes-related autoantibodies present on two separate samples, one of which was drawn within the past six months (210 days). Confirmation does not have to involve the same 2 autoantibodies.
6. Weight  $\geq$  12 kg at the time of screening.
7. If a female participant with reproductive potential, willing to avoid pregnancy and undergo pregnancy testing prior to randomization and at each study visit.
8. Anticipated ability to swallow study medication.

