#### **8.4. Study Power and Accrual Target**

This study has been designed to provide 83% power to detect a 50% risk reduction in the hazard rate for progression to Stage 2 or 3 T1D (abnormal glucose tolerance or diabetes diagnosis) using a two-sided test at the 0.05 level after a minimum of two years of follow-up on all participants and an expected total study duration (accrual and follow-up) of six years. We note that if accrual is more rapid than expected, minimum follow-up on participants may need to be extended in order to meet the number of events required for the final analysis.

A total of 201 participants will be randomized in a 2:1 allocation to treatment with hydroxychloroquine (n=135) vs. placebo (n=66). Randomization will be conducted using block randomization with variable block sizes with stratification on (1) whether or not participants have been previously treated for T1D prevention, and (2) age group (< 8 years old vs. 8 years old or older).

The assumptions underlying the estimated sample size for this design are: (1) 40% two-year event rate in the placebo group, (2) detectable hazard ratio of 0.50 (i.e. 22.5% two-year event rate) in the hydroxychloroquine group, (3) less than a 10% two-year dropout rate in both groups, and (4) survival curves which are consistent with exponential survival distributions. Even testing for variable proportions of each stratum and with slight variation in the expected hazard rates for the placebo group across the strata, our proposed sample size of 201 participants will provide at least 83% power to detect a hazard ratio of 0.50 in the time to T1D stage progression between the two treatment groups using a stratified Cox regression model.

Under the above assumptions, the target total number of events is equal to 80; i.e., the final analysis will be conducted once 80 events (confirmed abnormal glucose tolerance, diabetes) have been observed. If the accrual rate is 50 patients per year, with the above assumptions it is estimated that the enrollment period will last approximately 4 years with a total study duration of approximately 6 years (4 years of accrual + minimum of 2 years of follow-up) to provide a sufficient number of events to detect the assumed difference.

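### Earlier abnormal glucose tolerance is checked at entry but is missing from the primary model and from the named subgroup and covariate lists

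*Protocol*

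**What the plan says.** **Entry.** Protocol 3.3.1, item 4, requires a normal OGTT within 52 days before randomisation and adds: "If previous abnormal glucose tolerance, has had two consecutive OGTTs with normal glucose tolerance". Protocol 4.1 and footnote 2 of Appendix 1 repeat the rule. The earlier abnormality may have been a single test or a confirmed pair; the text neither requires nor excludes confirmation.

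**Cohort.** Protocol 8.1 speaks of the "primary analysis cohort consisting of participants with islet cell autoimmunity and absence of metabolic abnormalities (normal OGTT", and SAP Section 2 is similar. Protocol 2.1.2 defines Stage 1 as two or more autoantibodies with normal tolerance and sets no condition on the past.

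**Endpoint.** Time runs from randomisation to AGT confirmed on two sequential OGTTs, or to diabetes.

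**Models.** The primary Cox model is stratified by prior prevention treatment and age group in Protocol 8.2, and has age as a covariate in SAP Section 3. Protocol 8.3 names as possible modifiers age, gender, race/ethnicity, a first-degree relative with T1D, autoantibody status and titres, weight, BMI, C-peptide, insulin resistance and prior prevention treatment. SAP 4.1 and 4.2 add HbA1c, HLA, and glucose and insulin measures at study entry. Prior AGT is in none of these lists.

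**Route for additions.** The last paragraph of Protocol 8.2 lets further factors be defined before unmasking and separates them from post-hoc factors.

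**The concern.** Two participants with the same normal entry OGTT can differ in whether they have been abnormal before. Someone who has crossed the threshold once is plausibly nearer to crossing it again, and the protocol itself asks for a second normal test from such people. The entry glucose values in SAP 4.2 are normal for everyone, so they need not carry this history.

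Three things are at stake:

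- An unmodelled prognostic factor pulls the Cox hazard ratio (HR) slightly towards 1 and costs some power.
- If the drug works differently in participants with prior AGT, the overall HR averages two effects, and no named analysis would reveal it.
- If the question is first raised after unmasking, the answer is post hoc by the protocol's own rule.

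The planning rate does not settle how common or how influential this history is. The protocol's source figure is: "Two year risk of confirmed abnormal glucose tolerance is 38% among individuals with multiple autoantibody positivity and normal glucose tolerance at baseline". It does not say whether that group included people with earlier AGT.

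**Working it through.** **1. The plan's own figure.** Protocol 8.4 states: "This study has been designed to provide 83% power to detect a 50% risk reduction in the hazard rate", "using a two-sided test at the 0.05 level". Inputs from the same section: HR 0.50, 2:1 allocation (135 and 66), 80 events. By Schoenfeld's formula:

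- Events = (1.960 + 0.954)² / [(2/3)(1/3)(ln 0.5)²] = 8.49 / 0.1068 = 79.5, so 80.
- Power at 80 events = Φ(√(80 × 2/9) × 0.693 − 1.960) = Φ(0.963) = 83.2%; with the final critical value of 1.969, 83.0%.
- Two-year rate on drug = 1 − 0.60^0.5 = 22.5%, as stated.

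The design reproduces, and none of these figures depends on AGT history.

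**2. Validity.** AGT history precedes randomisation, so it is balanced in expectation. With no drug effect, three times the hazard and a 10 to 20% share, the simulated two-sided type I error was 5.1 to 5.2% (8,000 runs each).

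**3. Simulation.** From the protocol: 135 and 66 participants, entry at 50 per year (201/50 = 4.02 years), exponential times, 10% two-year dropout, analysis at the 80th event, critical value 1.969. Placebo participants without prior AGT have a 40% two-year rate, a hazard of −ln(0.60)/2 = 0.255 per year; the HR in participants without prior AGT is 0.50. Assumed, because the documents are silent: the prior-AGT share, their hazard multiple, and the drug HR in them. With no such participants the simulated power is 85.8%, somewhat above Schoenfeld's 83.0%, so changes are read against the simulation's own base.

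Unstratified Cox models, 2,500 to 3,000 runs per row (the row 6 HR: 4,000):

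| Share | Hazard multiple | HR in prior AGT | HR, no term | HR, with indicator | Power, no term | Power, with indicator |
|---|---|---|---|---|---|---|
| 10% | 2 | 0.50 | 0.508 | 0.501 | 84.8% | 85.8% |
| 20% | 2 | 0.50 | 0.512 | 0.502 | 83.4% | 84.3% |
| 20% | 3 | 0.50 | 0.526 | 0.499 | 80.9% | 85.6% |
| 10% | 2 | 0.75 | 0.536 | 0.532 | 78.0% | 78.6% |
| 20% | 2 | 0.75 | 0.568 | 0.564 | 69.6% | 68.9% |
| 20% | 2 | 1.00 | 0.613 | not computed | 56.6% | 52.4% |

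The adjusted HRs in rows 4 and 5 and the HR in row 6 come from separate runs of the same set-up. A repeat of row 5 gave 69.9% and 69.8%; a repeat of row 6 gave 56.7% and 53.2%. Each power figure has a Monte Carlo error of about √(0.85 × 0.15 / 2,500) = 0.7 points, so differences near 1 point should not be read closely.

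**4. Stratified model, 5 to 20% share, two to three times the hazard.** With a common HR of 0.50, the indicator moves the HR from 0.50–0.53 to 0.49–0.50 and adds about 0 to 6 points of power, mostly 1 or less. With HR 0.75 in prior AGT it is neutral. With no effect in prior AGT it loses about 3 points.

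**5. What adjustment cannot do.** In rows 4 and 5 the indicator hardly moves the HR, because the two groups truly differ. Restricting to participants with no prior AGT gives 0.502 and 0.500, against 0.536 and 0.568 overall. Only that restriction, or an interaction term, shows the difference.

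**6. Numbers available.** A 5 to 20% share of 201 is about 10 to 40 people, so an interaction test would be weak.

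**The case against.** The strongest defence is that nothing here is wrong. All entrants have a current normal OGTT, the outcome starts at randomisation, and the all-participant HR is the effect that the plan intends to estimate. The plan also has open routes: Protocol 8.2 allows factors to be added before unmasking, Protocol 8.3 covers metabolic factors in open-ended terms, and SAP 4.2 has treatment interactions and a step-up procedure. Nothing in the documents shows that AGT history predicts beyond HbA1c, C-peptide and the entry glucose measures. Under a common effect the gain is small, and under a weaker effect in prior AGT the indicator does not recover 0.50.

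Most of this stands. It disposes of any claim of bias, and it makes the sensitivity and interaction analyses at least as useful as the covariate. It does not supply the missing item: an open-ended list is not a pre-specified factor, and the route in Protocol 8.2 helps only if it is used before unmasking.

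A reader might also take the protocol's rationale as a forecast of weaker response in these people: "Intervention early in the course of disease is likely to be more effective than intervention in those with abnormal glucose tolerance". That sentence goes on to include clinical T1D and concerns present status. It does not address people who have returned to normal tolerance, so a weaker effect in them is a possibility to examine, not a prediction.

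**Conclusion.** The point holds as a minor improvement in precision and interpretation. A factor that eligibility already requires sites to check has no place in the planned analyses. Its size rests wholly on an assumed share, hazard multiple and effect in prior AGT: under a common effect usually a point of power or less, and about 6 at most in the range examined. The more informative gain is seeing any dilution, for example 0.57 overall against 0.50 in participants with no prior AGT (20% share, twice the hazard, HR 0.75 in them).

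Three stronger readings might be inferred, and the documents do not support them:

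- **That the cohort description contradicts eligibility.** Protocol 8.1 explains absence of metabolic abnormalities, in the same phrase, as a normal OGTT, and Stage 1 is a current state.
- **That recurrences are counted as first progression and bias the result.** The plan never calls the endpoint a first lifetime event. Prior AGT at entry need not have been confirmed whereas the endpoint must be, so some of these people never met the endpoint definition. History precedes randomisation in both arms.
- **That 83% power or 80 events is wrong.** Both reproduce.

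**What to change.** Before unmasking, by the route in Protocol 8.2:

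1. Derive one baseline indicator, any prior AGT (yes/no), from the OGTT history used to check criterion 4. Report single versus confirmed descriptively only.
2. Include the indicator as a covariate in the stratified primary Cox model.
3. Add it to the pre-specified treatment-by-subgroup interactions in SAP 4.1.
4. Pre-specify a sensitivity analysis in participants with no recorded prior abnormal OGTT.

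The wording of Protocol 8.1 and SAP Section 2 needs no correction; a cross-reference to inclusion criterion 4 is optional. Eligibility, enrolment, treatment and the event target do not change.

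Cost: SAP text, one derived variable and one model parameter. If the drug has no effect in participants with prior AGT, the covariate loses about 3 points of power. A record of no prior AGT may also mean only that few earlier tests were done, so the number of OGTTs before randomisation should be tabulated beside the indicator. If the sponsor prefers to leave the primary model alone, items 1, 3 and 4 still answer the question of interpretation.

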## 8.2. Primary Analysis

The primary objective of the study is to assess the effect of hydroxychloroquine therapy versus placebo on the risk of progression to Stage 2 or 3 T1D, which is measured from an OGTT or clinically diagnosed with confirmation.

Time to progression to Stage 2 or 3 T1D will be calculated across participants within each treatment group. Time to T1D stage progression will be estimated based on Kaplan-Meier methodology, where participants who were "free of abnormal glucose tolerance and/or T1D" at their last follow-up will be censored at that time point.

This time-to-event outcome will be analyzed using a Cox proportional hazards regression model that stratifies by prior T1D prevention treatment (none vs. placebo vs. active therapy) and age at the time of randomization (<8 yr vs  $\geq$ 8 yr), where treatment effect in this model will be tested using the Wald statistic. Incorporating these as stratification factors in the Cox regression model will allow separate baseline hazard functions to be fitted for each stratum. We will further evaluate differences in event rates in those in the prior treatment stratification factor; specifically, we will assess if there are differential event rates in those enrolling after participation in another prevention trial and ensure that this is accommodated by corresponding stratification in the Cox regression model.

In addition to stratifying on these factors, we will also evaluate if they are effect modifiers on any differences observed in the time to T1D stage progression between these prior treatment groups; i.e., we will formally test for interactions of treatment effect with prior treatment for T1D prevention as well as age on time to T1D stage progression (i.e. progression from Stage 1 to Stages 2 or 3 T1D).

Proportional hazards can be tested to ensure that we can assume that these effects will be parallel. If the assumption of proportional hazard is not appropriate, the data will be examined to determine the cause of non-proportional hazard, such as the presence of a decaying, diverging, or crossing effect of hazard ratios over time. Based on the cause of the non-proportional hazard, post-hoc analyses such as frailty models, parametric models, or models with interactions and time-dependent covariates may be employed.

Additional factors may be defined before unmasking of the study data to the investigators. The analyses will distinguish between factors specified prior to unmasking, and those identified post-hoc during

analysis. Data from the TrialNet Pathway to Prevention Study may be used to determine participant eligibility. Outcomes from other studies may be used in meta-analyses, but not in the evaluation of this study's efficacy.

